## **ABSTRACT**

**Background:** Chronic Obstructive Pulmonary Disease (COPD) is a problem of public health of great magnitude, increasing morbidity and mortality and of high cost both in health resource consumption and in loss of quality of life related to health (HRQL). The "comprehensive approach to this complex illness, promoting self-care, improves HRQL and the clinical situation of patients, as shown by several studies, but more studies are needed to corroborate these results in the " Primary Care Area " (PC), and to make clear recommendations about the most effective type of intervention.

**Hypothesis:** In patients with moderate to severe COPD, a self-care structured intervention is more effective than the usual intervention on the main variables associated with the disease: HRQL, pulmonary function, exacerbations, hospital admissions, in the setting of PC in a follow-up of 6, 12 and 24 months

**Objectives:** To evaluate the impact of a comprehensive intervention to promote self-care and improve HRQL in people with COPD in PC.

**Methods:** Randomized clinical trial multicentre with and control group, carried out at PC centers of Barcelona.

**Determinations:** specific questionnaires, standardized and validated, such as the St George's Respiratory for HRQL.

ifferences  
between groups and variance of repeated measures (ANOVA) will be used to evaluate the effect of the intervention.

**Expected results:** Significant improvement in HRQL in patients with COPD attributable to the intervention performed.

**Applicability and Relevance:** The intervention could be incorporated into regular clinical practice with standardized contents.

## **STUDY PROTOCOL**

### **1. BACKGROUND**

Chronic Obstructive Pulmonary Disease (COPD) is characterized by a chronic progressive air flow limitation which is not reversible and mainly associated with tobacco smoke. It is an illness that can be prevented and treated, with systemic involvement and usually accompanied by comorbidity.(1-7)

In recent years, COPD has been defined not only as a pulmonary obstructive disease but also as a disease with systemic repercussion, and phenotypes have been recognized depending on the clinical presentation. (1-9)

COPD is a public health problem of great magnitude, with high morbidity and mortality and a high health cost. The condition is under-diagnosed and its prevalence is expected to continue to increase. (8-9)

The study of global burden of the disease (Global Burden of Disease Study-GBD-) targeted globally,has detected an increase of people with COPD compared to 1990 of almost 120 million.(10)

In Spain, the IBERPOC study reported a prevalence of COPD of 9.1% among the population aged 40-69 years, with a high level of underdiagnosis: 78.2%. The "EPI-SCAN study" estimates the prevalence in the population of between 40 and 79 years in 10.2% with a 73% underdiagnosis. (11)

The mortality rate of COPD, according to the GBD of the WHO, went from the fourth place in 1990 to the third place in 2010. (10) In Spain, according to data from the Carlos III Health Institute, COPD is the fifth cause of mortality. (12) In Catalonia, according to data from the Department of Health 2009 COPD

is the third cause of death. (13)

COPD is associated with a high cost in both health resource consumption and a loss of quality of life related to health (HRQL). In Spain, according to the Ministry of Health and Consumption-2009, "the estimated direct, indirect and intangible costs of COPD are estimated at 750-1000 million euros / year. The average direct cost per patient is 1,712-3,238 euros / year distributed between 40-45% hospital costs, 35-40% in drugs and 15-25% in diagnostic tests. (14)

In Catalonia, according to the Catalan Health Service-2004, direct costs are estimated at 238.82 million euros / year. It originates 10-12% of the consultations in primary care, 10% of visits to pneumology and is the third cause of hospitalization (more than 12% of patients require patients a hospital admission every year and almost 25% of them an annual consultation. (15).

Given the complexity of the disease, a multidimensional approach allowing an integrated approach to control symptoms, slow down progression and reduce the number of exacerbations, is needed, with the aim of improving the prognosis and quality of life of people affected. Comprehensive care includes health education, rehabilitation, the promotion of self-care and the involvement of the patient in decision-making. (15)

Comprehensive care, according to the Terminology of Chronicity (TC), involves the complete interpretation of the human being and incorporates the promotion, prevention, recovery and rehabilitation to guarantee the global management of the person's needs, taking into account the multidimensional assessment (physical, emotional, cognitive, functional, social, ecological, spiritual and ethical aspects). (16)

Self-care is a term applied to educational programs aimed at acquiring the necessary skills to perform the specific therapeutic regime for the disease, guide the healthy behavioural change and provide emotional support to patients for the control of their illness and for living a functional life (17,18)

According to the Cochrane (RS) systematic review on "Self-care education for patients with COPD" (08/2007): "In COPD the value of self-care education is still unclear / .../ data is not enough to make clear recommendations about the form and contents of the self-care education programs for patients with COPD. " (19)

A new systematic Cochrane review (2014) concluded that interventions where self-care is promoted are associated with a better HRQL, a reduction in hospital admissions and an improvement in dyspnea scale, without finding significant differences in other parameters. However, the heterogeneity of the studies makes it difficult to make clear recommendations about the types of intervention in the self-care of COPD, and a review of the studies included demonstrates that there is little evidence within the scope of primary care.

There is an obvious need to carry out more large randomized clinical trials with long-term follow-up, before more conclusions can be made. (20)

The Catalonia Health Plan 2010-2015 already contemplated the need to implement structured clinical processes for COPD with guides and defined care routes, and reinforced the role of Primary Care in chronic care. It also emphasized the importance of strengthening patients' self-responsibility: "especially from Primary Care, measures should be provided to raise awareness of patients and caregivers, taking into account self-care opportunities".

The new Health Plan of Catalonia 2016-2020 gives continuity to the previous one, emphasizing also the self-responsibility and self-care of people to achieve greater autonomy, a higher degree of compliance and facilitate shared decision-making. One of the 11 goals and priorities of health, emphasizes the personalization of care in

respiratory diseases: “By 2020 a model of personalized medicine for COPD will be implemented in Catalonia. (21)

## **2. HYPOTHESIS AND OBJECTIVES**

Hypothesis: In patients with moderate to severe COPD, structured intervention in self-care is more effective than usual intervention in the main variables associated with the disease: quality of life, pulmonary function, exacerbations, hospital admissions, and primary care visits in a follow-up of 6, 12 and 24 months.

Overall objectives: To evaluate the impact of a comprehensive intervention to promote self-care and to improve the quality of life in people with Chronic Obstructive Pulmonary Disease (COPD) in Primary Care (PC).

Specific objectives: 1.- To describe the profile of patients with COPD in our area through the main sociodemographic characteristics (sex, age, level of studies), risk factors, COPD phenotypes, respiratory function, prognosis, pharmacological treatment, technique inhalation, exacerbations and hospital admissions, comorbidities, and quality of life.

2.-To assess using a clinical trial the effectiveness of a self-care program on different dimensions of clinical importance in COPD (degree of dyspnoea, prognosis, number of exacerbations, number of hospital admissions, degree of anxiety and depression).

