## **3. METHODOLOGY**

Design: Multicentre randomized clinical trial

Reference population: Patients with a diagnosis of moderate-severe COPD treated with inhaled bronchodilators.

Study population: Patients with a diagnosis of moderate and / or severe COPD , with bronchodilator treatment in PC Centers, that meet the criteria for inclusion in the study.

Inclusion criteria: Patients who have been visited at least once last year at the center with diagnosis of COPD (J44), with a moderate airflow limitation (FEV1 between 50% - 80%) or severe airflow limitation(FEV1 between 30 % - 50%), treated with bronchodilators, and who accept to participate in the study.

Exclusion criteria

- Patients only receiving home attention (Z74)
- Patients with mental disorders and / or severe mental disorders that do not allow following the sessions
- Patients diagnosed with asthma, tuberculosis or other chronic respiratory diseases
- Patients receiving chronic home oxygen therapy (OCD).
- Patients with terminal disease.

Sample size and sample procedure: Accepting an alpha risk of 0.05 and a beta risk lower than 0.2 in a bilateral contrast, 182 subjects in the first group and 182 in the second are need to detect a difference equal to or greater than 3.51 Units in the St George's Respiratory Questionnaire. It is assumed that the common standard deviation is 11.33. A follow-up loss of 10% has been estimated. Patients will be contacted by phone, via sms, internet or at office consultation (according to the authorization given to the e-CAP) by offering participation in the study and a visit will be scheduled to explain the study and to obtain the signed informed consent and the collection of data.

The random distribution to the groups will be carried out centrally, through a computer program that generates the random numbers managed by a remote investigator to recruiters. The allocation of each patient will be hidden in an envelope that will be opened when the professional has confirmed that he complies with the selection criteria and the patient has signed the informed consent.

Variables

-Quality related to Health (QVRS) will be measured with specific and standardized self-administered questionnaires, validated by our environment:

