-Degree of participation in the intervention: 1 session/ 2 sessions/ 3 sessions/ ≥ 4 sessions

All the variables studied will be collected at baseline, prior to the intervention, and at 6, 12 and 24 months later, both in the intervention and in the control groups.

The control group will follow the usual treatment and follow-up and a visit will be scheduled to obtain the same variables as the intervention group, on a first visit, and at 6, 12 and 24 months.

Collection of data and sources of information:

Data analysis: Analysis will be carried out by intention to treat basis. All patients who signed their informed consent and who have completed the initial evaluation will be included in the analysis. The descriptive statistics of dependent, confusing and general variables will be calculated, both for the intervention group and for the control group and the homogeneity of the two groups for these variables will be checked at the beginning of the study. In all cases, a bilateral alpha error of 0.05 will be considered and the confidence intervals will be calculated at 95%. A variable will be calculated for each

measurement time (baseline, 6 months post-intervention and 12 and 24 months), which is the difference between the result of SGRQ and the other dependent variables of interest in each cut and the initial value, for each individual. Differences between groups and the confidence intervals of the difference to 95% will be calculated. An analysis of the variance of repeated measures (ANOVA) will be performed to evaluate the differences in time of dependent variables attributable to the effect of the intervention. It will adjust for the possible confusers, comorbidity, other interventions carried out, among others.

Difficulties and limitations of the study: This is a clinical trial in which health professionals who usually see the subject of study can know the group to which the patient belongs. They will "try to preserve masking in some important stages of the study: random allocation, evaluation of the main measures, statistical analysis of the data. On the other hand, the duration of the study can lead to long term loss to follow-up. To ensure the patient's adherence telephone location will be performed (at least three attempts per appointment, if the patient has not indicated that he does not want to participate) when missing the intervention sessions and a quarterly reminder telephone contact.

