#### 4. APPLICABILITY AND PRACTICAL UTILITY OF THE RESULTS OF THE STUDY

**Clinical Impact:** The empowerment of the patient with COPD by facilitating his autonomy and self-responsibility will result in improved self-control of the disease and improvement in clinical outcomes. The application of knowledge from this research: structuring and standardizing the methods and contents of the nurse intervention in the COPD patient and their follow-up will also result in positive clinical outcomes.

**Practical utility of the results:** Adapting to our population interventions that have been shown to improve the quality of life and the clinical parameters of patients with COPD.

**Scientific and socioeconomic relevance:** This study will provide scientific evidence on the type of self-care intervention in patients with COPD in Primary Care that proves to be effective and will allow to formulate clear recommendations on how to carry out this intervention by the nurse. On the other hand, the expected improvement in the quality of life and in the clinical parameters of the patients with COPD will contribute to reduce the expenses attributable to this disease, both in health and social resources (maintenance of functional life that will minimize the loss of working days, for example)

**Bibliometric impact:** We believe that this study could generate a minimum of 3 communications in scientific meetings and 2 publications.

**Plan for the dissemination of results:** The results of the study that provide relevant information, will be presented at conferences and will be published in national and international journals of nursing and medicine with great bibliometric impact.

**Innovation and transfer plan:** The design of nursing training in order to carry out the intervention in our study, in an online format, can be spread to all the nursing staff in our surroundings in a fast way, to apply the methods and contents that have been proven effective in the usual care practise. The majority of the tests used in the data collection of the project, which are useful at the time of the intervention as they complement the patient's assessment, allows us to offer a more personalized attention and are perfectly implementable in the clinical practise (e-CAP). The use of new technologies is contemplated as they are part of our day to day practise and most patients use them, as a reinforcement of personal attention to the query.

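### Outcomes other than SGRQ are hypothesised and tested at two-sided 0.05 each, with no ranking, adjustment or exploratory label, so a positive result on one of them cannot carry a claim of effectiveness

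*Combined protocol and SAP*

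**What the plan says.** - **Hypothesis (section 2).** The protocol expects that the "structured intervention in self-care is more effective than usual intervention in the main variables associated with the disease". The list has five entries: quality of life, pulmonary function, exacerbations, hospital admissions and primary care visits, at 6, 12 and 24 months.
- **Specific objective 2 (section 2).** The aim is "To assess using a clinical trial the effectiveness of a self-care program on different dimensions of clinical importance in COPD". The dimensions are dyspnoea, prognosis, exacerbations, admissions, and anxiety and depression.
- **Sample size (section 3).** It is set to "detect a difference equal to or greater than 3.51 Units in the St George's Respiratory Questionnaire", with "Accepting an alpha risk of 0.05 and a beta risk lower than 0.2 in a bilateral contrast". No other outcome is sized.
- **Data analysis (section 3).** For each person the plan calculates "the difference between the result of SGRQ and the other dependent variables of interest in each cut and the initial value". It then gives between-group differences with 95% confidence intervals and a repeated-measures ANOVA. The error rule is general: "In all cases, a bilateral alpha error of 0.05 will be considered".
- **Use of the result (section 4).** The study is to provide evidence on the type of intervention "that proves to be effective and will allow to formulate clear recommendations on how to carry out this intervention by the nurse".

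Nowhere is an outcome called primary, secondary or exploratory. There is no testing order and no division of alpha.

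**The concern.** The hypothesis puts four other outcomes on the same footing as quality of life, and objective 2 adds three more (four if anxiety and depression are scored separately). Each is judged at the full 0.05. The plan does not say what pattern of results would support the hypothesis.

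The case that matters is a null SGRQ result with one other outcome, say dyspnoea, at p<0.05. Nothing in the text stops that from being reported as effectiveness, and section 4 intends to turn the finding into practice recommendations for nurses. With several outcomes tested in this way, an inert programme would produce such a result more often than the nominal error rate suggests.

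**Working it through.** **1. The plan's own figure.** Inputs from section 3: difference 3.51, SD 11.33, two-sided alpha 0.05, power 80%, loss 10%.

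n per arm = 2 × (1.96 + 0.8416)² × (11.33/3.51)² = 163.6, about 164. Allowing for loss, 163.6/0.9 = 181.7, so 182. The stated size is reproduced as one unadjusted two-sided SGRQ comparison, which confirms that SGRQ alone was sized.

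**2. Counting outcomes (section 2).**
- Hypothesis variables other than quality of life: pulmonary function, exacerbations, admissions, primary care visits. k = 4.
- Both lists together: add dyspnoea, prognosis, anxiety/depression. k = 7, or 8 with anxiety and depression separate. The second quality-of-life instrument, CAT, is not counted.

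**3. Chance of at least one false positive at one visit.** Assumptions, none of them given in the documents: no true effect on any outcome, normal test statistics, and equal correlation r between outcomes.
- Independent outcomes, either direction: 1 − 0.95^k. For k = 4 this is 1 − 0.8145 = 18.5%.
- Independent outcomes, favouring the intervention only: 1 − 0.975^k. For k = 4 this is 1 − 0.9037 = 9.6%.
- Correlated outcomes: the same probability for equicorrelated normal statistics with critical value 1.96, by numerical integration.

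| k | Direction | r = 0 | r = 0.5 | r = 0.7 |
|---|---|---|---|---|
| 4 | either | 18.5% | 15.6% | 13.0% |
| 7 | either | 30.2% | 23.0% | 17.8% |
| 8 | either | 33.7% | 25.0% | 19.1% |
| 4 | favourable | 9.6% | 7.8% | 6.5% |
| 7 | favourable | 16.2% | 11.5% | 8.9% |
| 8 | favourable | 18.3% | 12.5% | 9.5% |

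The nominal rate is 5% for the either-direction rows and 2.5% for the favourable rows. Some correlation is certain, because the variables list in section 3 builds BODEx from FEV1, dyspnoea and severe exacerbations, among others. The r = 0 column is therefore an upper bound among non-negative correlations.

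**4. Price of a Holm adjustment.** With 163.6 analysed per arm and 80% power, the detectable difference in SD units is √(2/163.6) × (z + 0.842).
- Unadjusted, z = 1.960: 0.31 SD.
- First Holm step with five outcomes, p ≤ 0.01, z = 2.576: 0.38 SD.
- First Holm step with eight outcomes, p ≤ 0.00625, z = 2.734: 0.40 SD.

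**The case against.** **SGRQ already has priority.** The overall objective speaks of quality of life, the abstract's expected result is an improvement in it, SGRQ alone drives the sample size, and the analysis text names SGRQ first and the rest as other dependent variables. This stands. A reader might infer that the trial's main conclusion is compromised, but the documents do not support that: the SGRQ test at a single visit is unaffected by what else is tested. Implicit priority still does not tell the reader how to treat the others, which the hypothesis lists as main variables.

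**The any-one reading is not in the text.** The hypothesis joins its variables with an *and*. If superiority on all of them were required, there would be no inflation. This also stands, so every rate above is conditional. The plan does not state the all-required reading either.

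**A multiple of three to four is tempting but needs care.** Set against the stated two-sided 0.05, the either-direction rate for the four hypothesis variables is 3.1 to 3.7 times nominal (15.6/5 to 18.5/5). That count includes results favouring control, which nobody would report as effectiveness. The favourable-only rate of 7.8% to 9.6% is 1.6 to 1.9 times 0.05. It is three to four times nominal only against the one-directional 2.5%.

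**The family is uncertain.** The variables list gives a stand-alone measure for only two of the four hypothesis variables, pulmonary function and admissions. With two outcomes the either-direction rate is 1 − 0.95² = 9.75% if independent and 9.1% at r = 0.5. The excess shrinks but remains.

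**Three visits.** A reader might multiply further across 6, 12 and 24 months. For the separate visits, however, the plan mentions differences with confidence intervals; the only test it names is the repeated-measures ANOVA. The figures here therefore stay at one visit.

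**Conclusion.** The point holds as a gap in how the non-SGRQ outcomes are governed. The plan hypothesises superiority on them, tests each at 0.05, and gives no ranking, adjustment or decision rule.

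If any one positive result is taken as support, then with no true effect, one visit and equal correlation of 0.5 to 0:
- either direction: about 16% to 19% for the four hypothesis variables, and 23% to 34% for both lists, against 5%;
- favouring the intervention: about 8% to 10% and 12% to 18%, against 2.5%.

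These are illustrations under assumptions, not properties that the documents state. They depend on the number of outcomes counted, the correlation and the direction, and these should be given beside any rate. The change should be made, but the matter does not invalidate the SGRQ conclusion.

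**What to change.** **Section 2.** Restrict the confirmatory hypothesis to SGRQ at one named visit. List every other outcome in the hypothesis and in objective 2 as secondary: pulmonary function, exacerbations, admissions, primary care visits, dyspnoea, prognosis, and anxiety and depression.

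**Section 3, data analysis.** Replace the general 0.05 rule. Use two-sided 0.05 for that one SGRQ comparison. Report all other outcomes and visits as estimates with 95% confidence intervals, labelled exploratory, with no claim of effectiveness.

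**If formal secondary claims are wanted.** List one secondary family in advance and test it at the same visit, only after a significant SGRQ result, with Holm at a total two-sided 0.05.

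**Cost.** Wording only; no extra patients or data. The exploratory option gives up secondary claims. The Holm option raises the detectable difference at its first step from about 0.31 SD to 0.38 SD with five outcomes, or 0.40 SD with eight, so a short family is preferable. The SGRQ sample size is unchanged.
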